3.1 General Design

This will be a Pilot study - single institution, two-arm, randomized, double blind study. Eligible study subjects will be enrolled among those being treated for mucosal head and neck squamous cell cancer receiving definitive or post-operative radiation therapy (photons or protons) and concurrent platinum-based chemotherapy in the Department of Radiation Oncology at the University of Pennsylvania. All study subjects will receive pregabalin or matching placebo starting the 1st day of radiation therapy and stopping upon resolution of acute mucositis pain following completion of therapy, approximately one month after the completion of radiation therapy. If it is not feasible to start pregabalin or matching placebo anytime following the 1st day of radiation treatments, patients may start pregabalin or matching placebo anytime following the 1st day of radiation treatment up through the end of the 2nd week of radiation treatment, so long as the patients still meet all eligibility criteria in Sections 4.2 and 4.3.

E		R ^a	
Ν		А	Arm 1 ^b
R		Ν	pregabalin target dose 300mg/day
0	Concurrent Chemo	D	starting concurrent with RT
L		Ο	-
L		Μ	Arm 2 ^b
М		Ι	Placebo
E		Ζ	starting concurrent with RT
Ν		Е	-
Т			

Version 06-01-2015 Page 11 a) Patients will be randomized prior to starting pregabalin or matching placebo on 1st day of radiation treatment. Patients may also start pregabalin or matching placebo anytime following the 1st day of radiation treatment up through the end of the 2nd week of radiation treatment, so long as all eligibility criteria in Sections 4.2 and 4.3 are still met.

b) See section 5.2 for details of treatment regimen

Follow-up – approximately 1 month post completion of radiation treatments for all study subjects

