5.2 Treatment Regimen

Study subjects will self-administer oral preparation of pregabalin or matching placebo in twice daily dosage. Study subjects may use capsule form or solution, depending on medical necessity.

All study subjects will start taking 75mg of pregabalin nightly starting on the first day of radiation treatments. The dose will be increased to 75mg twice daily on day 3 and subsequently to 150mg twice daily on day 5.

Study subjects randomized to the treatment arm will continue to take 150mg of pregabalin twice daily for the duration of their radiation treatments until approximately their one month follow up visit. Subjects will be instructed at their follow up visit on how to taper the study drug.

Subjects randomized to the placebo arm will receive capsules and/or liquid that looks identical to the treatment arm. Subjects will titrate and taper in a fashion identical to the treatment arm.

At the discretion of the treating physician/NP, the interval between increasing dosage may be prolonged to a maximum of 4 days or the dosage reduced after the goal dose has been reached. Participants reporting excessive sedation or dizziness will be allowed to delay dose escalation. If a patient is not able to reach or maintain the goal dose at any point during the study (such as due to an adverse event at least possibly related to the study drug), the patient may continue on study and will be included in the analyses. The dose reached/dose

CONFIDENTIAL

Page 14

reduction will be recorded by the treating physician/NP with annotation of the rationale for the decision to maintain at that dose.

During titration, patients will be assessed daily by designated study staff before or after their daily radiation treatment in order to discuss/report with/to the PI any adverse events associated with the study drug.

Patients will be screened for suicidal ideation by designated study staff at baseline, daily during week 1 titration of the study drug and on a weekly basis during the study period until chemotherapy and radiation therapy are completed. Patients will be screened for depression again at the 1 month inspection visit. All patients will be screened using the Depression Screening assessment (appendix H).

Patients scoring a 10 or higher or reporting anything other than a 0 on question # 5 will meet with a physician/NP and will be:

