(For example: A patient initiating LYRICA therapy for postherpetic neuralgia with normal renal function ($CLcr \ge 60$ mL/min), receives a total daily dose of 150 mg/day pregabalin. Therefore, a renal impaired patient with a CLcr of 50 mL/min would receive a total daily dose of 75 mg/day pregabalin administered in two or three divided doses.)

For patients undergoing hemodialysis, adjust the pregabalin daily dose based on renal function. In addition to the daily dose adjustment, administer a supplemental dose immediately following every 4-hour hemodialysis treatment (see Table 1).

Table 1. Pregabalin Dosage Adjustment Based on Renal Function Creatinine Clearance (CLcr) (mL/min)	Total Pregabalin Daily Dose (mg/day)*			Dose Regimen			
≥60	150	150 300 450 600 BID or TID					
30–60	75	150	225	300	BID or TID		
15–30	25-50	75	100-150	QD or BID			
<15	25	25-50	50-75	75	QD		
Sup	plementary	dosage fo	llowing hemo	odialysis (mg	z)†		
Patients on the 25 mg QD regimen: take one supplemental dose of 25 mg or 50 mg Patients on the 25–50 mg QD regimen: take one supplemental dose of 50 mg or 75 mg Patients on the 50–75 mg QD regimen: take one supplemental dose of 75 mg or 100 mg Patients on the 75 mg QD regimen: take one supplemental dose of 100 mg or 150 mg							

In this protocol, patients with a baseline GFR < 30 will be ineligible. Patients with GFR of 30-60ml/min (as determined by laboratory evaluation one week after chemotherapy and hydration) will have drug dose reduced to 75 mg, twice daily for the remainder of the study. Patients with a GFR < 30 will be removed from the study (also listed as exclusion criteria). Potential side effects associated with a quick taper far out weight the side effects of depression.

Hospitalization, Prolonged Hospitalization or Surgery

Any adverse event that results in hospitalization or prolonged hospitalization should be documented and reported as a serious adverse event unless specifically instructed otherwise in this protocol. Any condition responsible for surgery should be documented as an adverse event if the condition meets the criteria for and adverse event.

Neither the condition, hospitalization, prolonged hospitalization, nor surgery are reported as an adverse event in the following circumstances:

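### The fixed renal dose (75 mg twice daily at GFR 30-60) suits the 300 mg/day target but gives no reduction to a patient already held at that dose for intolerance

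*Combined protocol and SAP*

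**What the plan says.** The goal dose is 150 mg twice daily; the schema in Section 3.1 gives "pregabalin target dose 300mg/day". Section 5.2 builds up to it from 75 mg nightly, through 75 mg twice daily on day 3, to 150 mg twice daily on day 5.

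Section 5.2 also allows patients to stay below the goal. On tolerance during titration it says "Participants reporting excessive sedation or dizziness will be allowed to delay dose escalation". It then says "If a patient is not able to reach or maintain the goal dose at any point during the study", giving a drug-related adverse event as an example, "the patient may continue on study and will be included in the analyses". The treating physician/NP may lengthen the titration interval; the other discretion named is "or the dosage reduced after the goal dose has been reached".

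The renal rule appears twice, in Section 1.2.2 (Pharmacokinetics) and in Section 8.1 (Renal dose Taper). A patient with GFR 30-60 mL/min one week after chemotherapy and hydration "will have drug dose reduced to 75 mg, twice daily for the remainder of the study". Neither place refers to the dose the patient is taking at the time. Below 30 mL/min the patient leaves the study.

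Section 8.1 also reproduces the label's Table 1, whose 30-60 row is half of the row for clearance of 60 or more in every column. The example beside it takes a patient from 150 to 75 mg/day at a clearance of 50 mL/min.

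**The concern.** A fixed dose works as a reduction only for a patient who is above it. The protocol expects some patients to be at or below it, because they could not tolerate more, and keeps them on study. It also expects some to lose renal function, because all receive platinum and GFR is checked after chemotherapy.

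Where both happen in a patient held at 75 mg twice daily, the rule changes nothing while clearance falls, and drug exposure rises. That is contrary to the rule's stated purpose in 8.1, which is to limit dose-dependent adverse reactions when renal excretion is impaired. Dizziness and somnolence are the obvious candidates: Section 1.2.3 reports them in 31% and 22% of pregabalin patients, more often at higher doses, and as the reactions that most often led to withdrawal (4% each). What is at stake is the safety of a very few patients.

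**Working it through.** **Inputs from the documents**
- Target 300 mg/day; lower titration steps 150 and 75 mg/day (Section 5.2).
- Renal rule at GFR 30-60: 75 mg twice daily = 150 mg/day (1.2.2 and 8.1).
- Table 1 (8.1): clearance 60 or more, 150 / 300 / 450 / 600 mg/day; clearance 30-60, 75 / 150 / 225 / 300 mg/day.
- Elimination nearly proportional to creatinine clearance (1.2.2.2.2).
- Ten patients on active drug (7.2).

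**Assumptions, not in the documents**
- Baseline clearance 70, 90 or 110 mL/min.
- New clearance 59, 45 or 31 mL/min, spanning the 30-60 band.
- Share of patients held below target, and share falling to GFR 30-60: 10% to 30% each, independent.

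**Step 1. Reproduce the plan's figure.** The ratio of the two Table 1 rows is 75/150 = 150/300 = 225/450 = 300/600 = 0.5. For the target, 300 × 0.5 = 150 mg/day = 75 mg twice daily. The rule agrees exactly with Table 1.

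**Step 2. Apply the rule at the dose being taken.**

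| Current dose (mg/day) | Rule gives | Change | Current dose × 0.5 |
|---|---|---|---|
| 300 | 150 | -50% | 150 |
| 225 | 150 | -33% | 112.5 |
| 200 | 150 | -25% | 100 |
| 150 | 150 | 0% | 75 |

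The 200 and 225 rows are not doses named in the protocol; they could arise only by discretion. At 150 mg/day, a defined titration step, the reduction is nil.

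**Step 3. Relative exposure.** Taking exposure as proportional to dose/clearance:

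ratio = (new dose / new clearance) ÷ (old dose / baseline clearance)

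For a patient held at 150 mg/day:

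| Baseline clearance | Dose unchanged, new clearance 59 / 45 / 31 | Halved to 75 mg/day, new clearance 59 / 45 / 31 |
|---|---|---|
| 70 | 1.19 / 1.56 / 2.26 | 0.59 / 0.78 / 1.13 |
| 90 | 1.53 / 2.00 / 2.90 | 0.76 / 1.00 / 1.45 |
| 110 | 1.86 / 2.44 / 3.55 | 0.93 / 1.22 / 1.77 |

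The central case is (150/45) ÷ (150/90) = 2.00. In that case the exposure equals the exposure on the dose not tolerated: 150/45 = 300/90 = 3.33. For comparison, the target patient cut from 300 to 150 mg/day from baseline 90 has ratios 0.76 / 1.00 / 1.45, so the rule does its job there.

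**Step 4. Absolute level.** The dose at clearance 90 that gives the same exposure as 150 mg/day at the lower clearance is 150 × 90 / new clearance: 229, 300 and 435 mg/day at 59, 45 and 31. All lie within the 150-600 mg/day range in Section 1.4.

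**Step 5. How many patients.** Expected number = 10 × p × q, where p and q are the two shares: 10 × 0.1 × 0.1 = 0.1; 10 × 0.2 × 0.2 = 0.4; 10 × 0.3 × 0.3 = 0.9. Fewer than one throughout.

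**The case against.** The strongest reply is that the gap is small and largely covered.

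- **Other provisions.** Section 8.1 reproduces Table 1 and an example that takes 150 to 75 mg/day, so a careful clinician has the right figure to hand. Section 5.2 makes the dose of a dose-limited patient an individual decision, recorded with its reason. It also halves the dose, on the way to stopping, after an unanticipated event. Section 8.1 mentions a change of dose when a laboratory result needs active management, and the investigator may withdraw a patient for safety.
- **Monitoring.** Laboratory tests every 1-2 weeks and weekly toxicity assessment during treatment would show both the decline and the symptoms.
- **Intolerance may pass.** Section 1.2.3 says dizziness and somnolence usually began early and lasted to the final dose in only 30% and 42% of those affected. A patient who could not tolerate 300 mg/day in week 1 may tolerate that exposure later, and it is the trial's own target exposure.

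Most of this stands, and it limits the point to a minor one. It does not close the gap, because none of these provisions prescribes a reduction below 75 mg twice daily when renal function declines. The example in 8.1 is label text for a patient starting therapy, and the protocol's own sentence then sets the fixed dose. Withdrawal is a blunt substitute for halving. The schedule in 6.5 lists no chemistry at the follow-up visit, although dosing continues for about four weeks after radiotherapy.

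Two stronger readings are tempting. A reader might infer that the rule contradicts Table 1. It does not: the table is entered with the recommended dose for the indication, and 300 gives 150 mg/day. A reader might also infer that a patient held at 75 mg nightly would have the dose raised to 75 mg twice daily. The rule speaks of reducing the dose, so that reading is unlikely. For this patient the rule simply gives no instruction, and 75 mg/day is already the lowest entry in Table 1's 30-60 row.

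**Conclusion.** The point holds as a minor safety gap. The rule is correct at the 300 mg/day target and gives no reduction to a patient held at 75 mg twice daily for intolerance. Under dose/clearance proportionality, that patient's exposure rises 2.0-fold when clearance falls from 90 to 45 mL/min. It rises between 1.2-fold and 3.5-fold over the assumed clearances; the upper end pairs the highest assumed baseline with a clearance just above the removal threshold. Halving the dose would give 1.0-fold, with a range of 0.6 to 1.8.

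The resulting exposure is not extreme in absolute terms. The harm is a return to a level the patient once could not tolerate, and continued intolerance is itself an assumption. The documents give neither the share of patients held below target nor the share reaching GFR 30-60, so the expected 0.1 to 0.9 active patients rests wholly on assumed rates and independence.

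A reader might infer that the gap threatens the trial's results. It does not: Section 7.5 plans only means, standard deviations and dropout counts, and Section 5.2 already keeps dose-limited patients in the analyses. The change is worth making because it costs almost nothing and makes the response uniform across prescribers.

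**What to change.** Replace the GFR 30-60 sentence in Sections 1.2.2 and 8.1, with a cross-reference in 5.2:

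> At GFR 30-60 mL/min the dose will not exceed 75 mg twice daily. A patient already held at 75 mg twice daily because of intolerance will be reduced to 75 mg/day (37.5 mg twice daily as oral solution, or 75 mg nightly). A patient at 75 mg nightly will not be raised because of this rule; further reduction is at the physician/NP's discretion.

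Apply it identically to placebo.

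Of the two options, 37.5 mg twice daily keeps to Table 1's divided regimen but is not a listed capsule strength. It needs 37.5/20 = 1.875 mL of the 20 mg/mL solution per dose. The nightly option uses an existing titration step but is once daily. Liquid drug and placebo are both available, and Section 5.2 says "Study subjects may use capsule form or solution, depending on medical necessity". Section 1.2.1 names only nothing-by-mouth status and inability to swallow pills as reasons for the liquid, so the pharmacy instruction should add renal dosing.

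The cost is a short text in two sections, a cross-reference and that instruction, with no extra patients, visits or tests. Staff must record when a patient is being held for intolerance; Section 5.2 already requires the dose and the reason to be noted. The downside is slightly lower drug exposure in a very few active-arm patients.

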8.2 Recording of Adverse Events

At each contact with the subject (see Section 6.5), the investigator/provider must seek information on toxicity/adverse events (see Section 8.1) by specific questioning and, as appropriate, by examination. Information on all toxicity/adverse events should be recorded immediately in the source document, and also in the appropriate toxicity/adverse event module of the case report form (see Appendix D). All clearly related signs, symptoms, and abnormal diagnostic procedures results should recorded in the source document, though should be grouped under one diagnosis, if possible.

All adverse events that would constitute toxicity from the study drug occurring during the study period must be recorded. The clinical course of each event should be followed until resolution, stabilization, or until it has been determined that the study treatment or participation is not the cause. Serious adverse events that are still ongoing at the end of the study period must be followed up to determine the final outcome.

All adverse events that would constitute toxicity from radiation therapy (photons or protons) and/or concurrent platinum-based chemotherapy during the study period will not be recorded. Though radiation therapy (photons or protons) and concurrent platinum-based chemotherapy are required for inclusion in this study, these treatments are not the interventions being examined nor are they included within the study objectives (Section 2).

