At screening, any clinically significant abnormality should be recorded as a preexisting condition. At the end of the study, any new clinically significant findings/abnormalities that meet the definition of an adverse event must also be recorded and documented as an adverse event.

Post-study Adverse Event

All unresolved adverse events should be followed by the investigator until the events are resolved, the subject is lost to follow-up, or the adverse event is otherwise explained. At the last scheduled visit, the investigator should instruct each subject to report any subsequent event(s) that the subject, or the subject's personal physician/NP, believes might reasonably be related to participation in this study.

Abnormal Laboratory Values

A clinical laboratory abnormality should be documented as an adverse event if any one of the following conditions is met:

- The laboratory abnormality is clinically significant and not otherwise refuted by a repeat test to confirm the abnormality
- The abnormality suggests a disease and/or organ toxicity
- The abnormality is of a degree that requires active management; e.g. change of dose, discontinuation of the drug, more frequent follow-up assessments, further diagnostic investigation, etc.

Renal dose Taper

In view of dose-dependent adverse reactions and since LYRICA is eliminated primarily by renal excretion, adjust the dose in patients with reduced renal function. Base the dose adjustment in patients with renal impairment on creatinine clearance (CLcr), as indicated in Table 1. To use this dosing table, an estimate of the patient's CLcr in mL/min is needed. CLcr in mL/min may be estimated from serum creatinine (mg/dL) determination using the Cockcroft and Gault equation:

$$CLCr = \frac{[140 - age (years)] \times weight (kg)}{72 \times \text{ serum creatinine (mg/dL)}} (\times 0.85 \text{ for female patients})$$

Next, refer to the Dosage and Administration section to determine the recommended total daily dose based on indication, for a patient with normal renal function (CLcr \geq 60 mL/min). Then refer to Table 1 to determine the corresponding renal adjusted dose.

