8.3 Reporting of Serious Adverse Events

8.3.1 IRB Notification by Investigator

Reports of all serious adverse events/adverse events (including follow-up information) that are BOTH unexpected and probably or definitely related to the study must be submitted to the IRB within 10 business days. Exception: If the adverse event involved a death and indicates that participants or others are at increased risk of harm, investigators are required to submit a report to the IRB within 3 days. Copies of each report and documentation of IRB notification and receipt will be kept in the Clinical Investigator's binder.

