8.3.2 DSMC Notification by Investigator

All events meeting the DSMC reporting requirements must be entered into the mandatory Velos AE/SAE **form.** Once an event is reported, you must keep the information accurate and current in Velos. If new/updated information is learned about the event, the event should be amended or corrected promptly. Only an investigator may determine the grade, attribution and expectedness.

On-Site subjects (this includes any subjects enrolled at other sites on an in-house study)

- 1. All grade 3 or higher events (AE or SAE) within 10 business days of knowledge.
- 2. All unexpected deaths within 24 hours of knowledge.
- 3. All others deaths within 30 days of knowledge. Deaths of subjects who are off study for more than 30 days from their last study treatment/intervention are not reportable with the following exceptions:
 - a) Deaths on in-house gene or cellular-therapies
 - b) Deaths on in-house studies utilizing on-campus manufacturing of the study agent(s) or components of the study agent(s)
 - c) Deaths on first-in-human studies

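### Section 8.2 bars recording of chemoradiation toxicity, which conflicts with the grade 3 or higher rule in 8.3.2 and, less sharply, with the laboratory rule in 8.1, and sets no relatedness level for mixed-cause events

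*Combined protocol and SAP*

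**What the plan says.** Section 8.2 has three parts. It opens with a general rule: "Information on all toxicity/adverse events should be recorded immediately in the source document", and also in the case report form. Its second paragraph is specific to the study drug: "All adverse events that would constitute toxicity from the study drug occurring during the study period must be recorded". Each such event is followed until it resolves or stabilises, or "until it has been determined that the study treatment or participation is not the cause". The third paragraph is the exclusion: toxicity from radiation and/or "concurrent platinum-based chemotherapy during the study period will not be recorded". The reason given is that these treatments are not the interventions under study and are not part of the objectives.

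Section 8.3.2 requires DSMC notification of "All grade 3 or higher events (AE or SAE) within 10 business days of knowledge", and of deaths within stated limits. Events that meet these requirements must be entered in the Velos AE/SAE form. It adds: "Only an investigator may determine the grade, attribution and expectedness".

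Section 8.1, under Abnormal Laboratory Values, lists three conditions, any one of which makes a laboratory abnormality an adverse event. The third begins: "The abnormality is of a degree that requires active management; e.g. change of dose, discontinuation of the drug".

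Section 3.6 makes clinician-reported toxicity, scored by CTCAE, the primary safety endpoint.

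**The concern.** Every patient receives radiation and platinum, so chemoradiation toxicity will be the commonest kind of event in this trial. For a severe one, a coordinator reads in 8.2 that it is not recorded and in 8.3.2 that it must be entered and sent to the DSMC. For a milder event that could have either cause, 8.2 supports both recording and omission. What reaches the safety data then depends on which section is read and on an attribution made without a stated threshold. The pilot is meant to inform a larger randomised trial, and a toxicity count filtered in this way would be hard to interpret or to carry forward.

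**Working it through.** The plan states no figure on this point, so the check compares the rules.

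1. **8.2 against 8.3.2.** Take a grade 3 event that the investigator attributes to chemoradiation. Under the third paragraph of 8.2 it is not recorded. Under 8.3.2 it is reportable within 10 business days and must be entered in Velos. Section 8.3.2 has no attribution limit. The omission is informative, because 8.3.1, immediately before it, does have one: IRB reports are confined to events "BOTH unexpected and probably or definitely related to the study". The protocol states a relatedness limit where it wants one. Section 8.3.2 does not defer to 8.2, and no other section gives an order of precedence.

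2. **8.2 against the laboratory rule in 8.1.** The protocol supplies its own case. Sections 1.2.2 and 8.1 say that a GFR of 30-60 mL/min, measured one week after chemotherapy and hydration, changes the study-drug dose. That meets the active-management condition, so 8.1 calls for it to be documented as an adverse event. If it is attributed to platinum, 8.2 says not to record it. By contrast, the hospitalization rule in 8.1 allows for contrary instructions elsewhere in the protocol. The laboratory rule has no such clause.

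3. **Mixed causes.** Section 1.2.3 associates pregabalin with a fall in platelets, and platelet decrease is a printed term on Appendix D. A grade 1-2 fall in a patient on platinum can be read as toxicity of either treatment, so it meets both the second and the third paragraphs of 8.2. The second paragraph leans towards recording while the cause is open, but it names no relatedness level. A level of at least possible relatedness appears in the withdrawal rule (grade 4-5 toxicity) and in 5.2 (patients who cannot reach or hold the goal dose). Neither is a recording rule. Grade 3 or higher platelet falls are less exposed, because 1.2.3, 5.2 and 8.3.2 all act on them.

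4. **How often step 1 could arise.** Section 1.1.4 cites a study with grade 3-4 mucositis in 85% of 126 patients and 77% of 65 patients.
   - Lower rate: 0.77 × 20 = 15.4 patients.
   - Weighted rate: (0.85 × 126 + 0.77 × 65) / 191 = 157.15 / 191 = 82.3%; 0.823 × 20 = 16.5 patients.
   - Upper rate: 0.85 × 20 = 17.0 patients.

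   This assumes that the cited rates apply here and that the grades correspond to CTCAE. Section 1.1.4 does not name the grading scale, and by its title the cited study included patients treated without chemotherapy. The figures show how often the two rules could collide, not how much information would be lost.

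5. **Size of the loss.** The documents give no shares for attribution to study drug, radiation or platinum, so no loss can be calculated.

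**The case against.** The strongest defence is that the exclusion is a deliberate, study-specific exception with its reason stated, while 8.3.2 reads like institutional template text: it covers other sites, gene therapies and first-in-human studies, none of which fits this trial. On that view the specific rule governs. This reconciles the exclusion with the opening of 8.2, so I do not count those two as contradictory. It does not settle 8.3.2 or the laboratory rule, which are in force as written and do not yield to 8.2.

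A second defence is that recording in 8.2 means the source document and toxicity module, whereas 8.3.2 concerns a separate DSMC form, so both can be obeyed. That reading is available but doubtful: 9.3 puts the electronic case report forms in Velos too, fed from the source documents.

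On laboratory values, 5.2 has the clinician record dose reductions with the rationale, so a laboratory-driven reduction leaves a trace even if no adverse event is recorded. This stands and makes the second conflict milder. The trace is a dosing note, though, and would not enter a toxicity count.

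On mixed causes, patient, coordinator and treating clinician are blinded (7.2), which limits differential attribution between arms. That stands too, although blinding does not recover an unrecorded event.

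A reader might go further and infer that low-grade pregabalin effects missing from Appendix D's printed list, such as peripheral edema or creatine kinase elevation, would be lost. The documents do not support this. They describe both only as pregabalin effects and link neither to radiation or platinum, so the second paragraph of 8.2 already requires them, and Appendix D asks for a description of any toxicity. Nor can much be made of the absence of an attribution line on that form, since form content may have been lost in text extraction.

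**Conclusion.** The point holds on the text and should be fixed. The conflict between 8.2 and 8.3.2 is direct for any grade 3 or higher event attributed to chemoradiation. The conflict with the laboratory rule is real but softer. Mixed-cause events have no stated relatedness level, which matters mainly for grade 1-2 events such as a modest platelet fall.

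The consequence is bounded. The loss to the safety endpoint is unknown and could be small. The analysis is descriptive (7.5), so no test or error rate is affected. Mucositis pain is captured separately by the OMQ and BPI (3.5), and the primary opioid data are unaffected. It would be wrong to conclude that toxicity will be biased between arms or that known pregabalin effects will go missing. What is shown is that the plan gives incompatible instructions and no order of precedence. That conclusion does not depend on the mucositis rates.

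**What to change.** Reword the exclusion in 8.2 so that:

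- (a) all grade 3 or higher events, deaths reportable under 8.3.2, serious events (subject to the hospitalization exclusions already in 8.1) and laboratory abnormalities that meet the 8.1 rule are recorded regardless of presumed cause;
- (b) any event of any grade that is at least possibly related to study drug, the level already used in 5.2 and the withdrawal rule, is recorded even if chemoradiation is the likelier cause, with the investigator's attribution noted;
- (c) only non-serious grade 1-2 events outside (a) and (b), judged unrelated to study drug, may be left out.

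Add a sentence to 7.5, which at present does not mention toxicity, saying that recorded events will be tabulated descriptively by arm regardless of attribution.

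The cost is a change of wording and a little extra data entry for 20 patients. Most of that is grade 3 or higher events that 8.3.2 already requires. The rest is chiefly chemotherapy-related laboratory abnormalities that 8.1 already covers, from blood tests taken every 1-2 weeks as standard care. The exclusion keeps its evident purpose of sparing staff routine low-grade chemoradiation effects. No dose or clinical-management rule changes.
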